#### **VISUAL ACUITY CONVERSION TABLE:**

SNELLEN	SNELLEN (METRIC)	logMAR	DECIMAL
No equivalent value 			
 20/20000	6/6000	3.0	0.001
 20/2000	6/600	2.0	0.010
20/400	6/120	1.3	0.05
20/320	6/96	1.2	0.063
20/250	6/76	1.1	0.08
20/200	6/60	1.0	0.10
20/160	6/48	0.9	0.125
20/150			
20/125	6/38	0.8	0.15- 0.16
20/100	6/30	0.7	0.20
20/80	6/24	0.6	0.25
20/70			
20/63	6/20	0.5	0.3- 0.32
20/60			
20/50	6/15	0.4	0.40
20/40	6/12	0.3	0.50
20/32	6/10	0.2	0.6-0.63
20/30			0.67 - 0.7
20/25	6/7.5	0.1	0.80- 0.9
20/20	6/6	0.0	1.00
20/16	6/5	-0.1	1.2 - 1.25
20/12.5			1.5- 1.6
20/10			2.0

1. Hand motion at 2 feet.

#### 5.2.4 Corneal Supportive Care Guidelines for Belantamab Mafodotin

Corneal events, which commonly manifest as superficial keratopathy, have been observed with antibody drug conjugates, including those conjugated to MMAF. As there is no single term which adequately captures these events, the term "corneal events" includes preferred terms describing corneal events reported with belantamab mafodotin, such as superficial punctate keratopathy, microcyst-like changes, subepithelial haze, corneal erosions and corneal ulcers.

Sites are required to establish a close collaboration with a qualified eye care specialist who will be responsible for assessing participants and managing those who develop corneal examination findings in close communication with the MCW PI (cc: MCW Multisite Team email).

Participants will be assessed by a qualified eye care specialist at screening/baseline and then prior to every dosing of belantamab mafodotin, and 70-day safety visit (assessment window of up to five days prior to dosing, but all effort should be made to schedule as close to belantamab mafodotin dosing as possible).

• If a participant subsequently develops vision changes or other ocular symptoms, the participant should be evaluated by a qualified eye care specialist.

2. Counting fingers at 2 feet.

3. Holladay JT. Visual acuity measurements. J Cataract Refract Surg. 2004; 30:287-290

4. Non-snellen acuity of 'light perception' or 'no light perception' do not have corresponding values.

- In case of persistent ophthalmologic exam findings, newly developed ocular symptoms or vision changes, the participants will have further ophthalmologic exams, at least every cycle until resolution (to grade 1 or baseline) or more frequently as clinically indicated by a qualified eye care specialist.
- Participants who have corneal signs per the Keratopathy Visual Acuity (KVA) scale for treatmentrelated corneal toxicities present at the end-of-study treatment will continue to be followed every three months for up to 12 months, or until full resolution of findings, which is defined as a return to participant's baseline, or until deemed clinically stable by a qualified eye care specialist, whichever comes first.

#### **Ocular Examination and Procedures**

Patients will be assessed by ophthalmologist (or an optometrist if an ophthalmologist is not available). A full screening/baseline ophthalmic examination for all participants must include for both eyes (OU), but is not limited to:

- 1. Best corrected visual acuity.
- 2. Documentation of manifest refraction and the method used to obtain best corrected visual acuity.
- 3. Current glasses prescription (if applicable).
- 4. Selected anterior segment (slit lamp) examination with focus on the cornea and lens, including fluorescein staining of the cornea.
- 5. Intraocular pressure measurement.
- 6. Dilated funduscopic exam.

The *on-treatment* and *follow-up* ophthalmic exam should be performed for both eyes (OU), as described below and in the schedule of assessments:

- 1. Best corrected visual acuity.
- 2. Documentation of manifest refraction and the method used to obtain best corrected visual acuity.
- 3. Slit anterior segment (slit lamp) examination with focus on the cornea and lens, including fluorescein staining of the cornea.
- 4. Intraocular pressure measurement (if clinically indicated).
- 5. Dilated funduscopic exam (if clinically indicated).

All ocular exam procedures/tests (e.g., BCVA, slit lamp, etc.) performed at screening/baseline exam should also be obtained at the next ocular exam obtained following treatment discontinuation (e.g., 70-day safety visit). Participants with corneal signs or symptoms at the 70-day safety visit will be followed at least every three months until resolution (to grade 1 or baseline) or more frequently as clinically indicated by the eye care specialist or up to one year (whichever comes first). Clinically stable is defined as changes less than or equal to grade 1 for both Ophthalmic Exam Findings and Visual Acuity according to the Keratopathy Visual Acuity (KVA) Scale criteria for eye disorders. Additional examinations should be performed at the discretion of the treating eye specialist.

#### **Ocular Prophylaxis**

Ocular prophylaxis should be instituted for all participants. Ocular prophylaxis includes:

Prophylactic preservative-free artificial tears must be administered in each eye at least four to eight times daily, beginning on cycle 1 day 1 until the end of belantamab mafodotin treatment.

Participants must not use contact lenses during the study, unless directed by an ophthalmologist (refer to Section 5.6).

#### Ocular Monitoring — Changes in Corneal Epithelium: Severity Grading and Mitigation Strategy

In order to minimize the changes in corneal epithelium associated with belantamab mafodotin, patients must receive prophylactic preservative-free artificial tears. The recommended administration is to use one drop in each eye at least four to eight times daily, beginning on cycle 1 day 1 until the subject discontinues treatment. In the event of ocular symptoms (e.g., dry eyes), the use of artificial tears may be increased up to every two hours as needed.

Corticosteroid eye drops are not required but can be used if clinically indicated per discretion of an eye care specialist. Allow at least five to 10 minutes between administration of artificial tears and steroid eye drops (if administered).

An ophthalmology or optometry (if ophthalmology is not available) consult is required for all patients who develop signs or symptoms of changes in corneal epithelium or require steroid eye drops for more than seven days.

[figure not shown]
Changes in corneal epithelium must be graded according to the KVA scale (Table 5).

#### 5.3 Safety Stopping Criteria

#### **Liver Chemistry Stopping Criteria**

Liver chemistry stopping and increased monitoring criteria have been designed to ensure participant safety and evaluate liver event etiology. Discontinuation of study treatment for abnormal liver tests is required when the participant satisfies any of the stopping rules as shown in the figure below.

#### Liver chemistry stopping and increased monitoring algorithm for subjects WITH entry criteria ALT ≤2.5xULN

- Must refer to Liver Safety Required Actions and Follow up Assessments section in the Appendix
- Report within 24 hours
- > If possible Hy's Law case: ALT≥3xULN and total bilirubin ≥2xULN (>35% direct) or INR>1.5\* report as an SAE

\*INR value not applicable to participants on anticoagulants

#### Phase I/II liver chemistry stopping and increased monitoring criteria

Liver chemistry stopping criteria (for patient treatment)				
ALT - absolute	$ALT \ge 5xULN$			
ALT Increase	ALT $\geq$ 3xULN persists for $\geq$	four weeks		
Bilirubin 	ALT $\geq$ 3xULN and total bil	irubin ≥ 2xULN (>35% direct bilirubin)		
INR 	ALT $\geq$ 3xULN and INR>1	5		
Cannot Monitor	ALT $\geq$ 3xULN and cannot be	be monitored weekly for four weeks		
Symptomatic 	ALT $\geq$ 3xULN associated w	$ALT \ge 3xULN$ associated with symptoms (new or worsening) believed to be		
	related to liver injury or hyp	ersensitivity		
Re	equired Actions, Monitoring	, and Follow-up Assessments		
Actions	ctions Follow-upp Assessments			
• Immediately discontinue study intervention. • Viral hepatit		• Viral hepatitis serology. 		
• Report the event to study PI within 24 hours		Obtain INR and recheck with each liver		
(refer to reporting secti	on).	chemistry assessment until the		
• Complete the requirement in reporting section		aminotransferases values show downward		
and complete SAE if the event also meets the		trend.		
criteria for an SAE. 		• Serum creatine phosphokinase (CPK) and		
• Perform liver event follow-up assessments as		lactate dehydrogenase (LDH), gamma glutamyl		
described in the follo	w-up assessment column.			

\*NOTE – in diagram above, "Appendix" is listed below in this section.

#### **Liver chemistry stopping criteria (for patient treatment)**

• Monitor the participant until liver chemistries resolve, stabilize, or return to within baseline (see **MONITORING**).

#### **MONITORING:**

## If ALT≥3xULN AND total bilirubin ≥ 2xULN or INR >1.5:

- Repeat liver chemistries (include ALT, AST, alkaline phosphatase, total bilirubin, and INR) and perform liver event follow-up assessments within 24 hours.
- Monitor participants twice weekly until liver chemistries resolve, stabilize or return to within baseline.
- A specialist or hepatology consultation is recommended.

## For all other criteria (bilirubin <2xULN and INR ≤1.5):

- Repeat liver chemistries (include ALT, AST, alkaline phosphatase, total bilirubin, and INR) and perform liver event follow-up assessments within 24 to 72 hours.
- Monitor participants weekly until liver chemistries resolve, stabilize or return to within baseline.

- transferase [GGT], glutamate dehydrogenase [GLDH], and serum albumin.
- Fractionate bilirubin, if total bilirubin >2xULN.
- Obtain complete blood count with differential to assess eosinophilia.
- Record the appearance or worsening of clinical symptoms of liver injury, or hypersensitivity, on the liver event form.
- Record use of concomitant medications on the concomitant medications report form including acetaminophen, herbal remedies, recreational drugs and other over the counter medications.
- Record alcohol use.

# If ALT ≥3xULN AND total bilirubin ≥2xULN or INR >1.5 obtain the following in addition to the assessments listed above:

- Anti-nuclear antibody, anti-smooth muscle antibody, type 1 anti-liver kidney microsomal antibodies, and quantitative total immunoglobulin G (IgG or gamma globulins).
- Serum acetaminophen adduct assay should be conducted (where available) to assess potential acetaminophen contribution to liver injury unless acetaminophen use is very unlikely in the preceding week (e.g., where the participant has been resident in the clinical unit throughout).
- Liver imaging (ultrasound, magnetic resonance, or computerized tomography) to evaluate liver disease.
- Liver biopsy may be considered and discussed with local specialist if available, in the following instances:
- o In participants when serology raises the possibility of autoimmune hepatitis (AIH).
- o In patients when suspected DILI progresses or fails to resolve on withdrawal of study intervention.
- o In participants with acute or chronic atypical presentation:
- If liver biopsy conducted collect all applicable data and report information to study PI (and MCW Multisite Team).
- 1. Serum bilirubin fractionation should be performed if testing is available. If serum bilirubin fractionation is not immediately available, discontinue study intervention for that participant if  $ALT \ge 3xULN$  and

- total bilirubin  $\geq 2xULN$ . Additionally, if serum bilirubin fractionation testing is unavailable, **record presence of detectable urinary bilirubin on dipstick**, indicating direct bilirubin elevations and suggesting liver injury.
- 2. All events of ALT ≥ 3xULN and total bilirubin ≥ 2xULN (>35% direct bilirubin) or ALT ≥ 3xULN and INR>1.5, which may indicate severe liver injury (possible "Hy's Law"), must be reported as an AESI (excluding studies of hepatic impairment or cirrhosis); the INR threshold value stated will not apply to participants receiving anticoagulants.
- 3. New or worsening symptoms believed to be related to liver injury (such as fatigue, nausea, vomiting, right upper quadrant pain or tenderness, or jaundice) or believed to be related to hypersensitivity (such as fever, rash, or eosinophilia).
- 4. Hepatitis A IgM antibody; hepatitis B surface antigen and hepatitis B core antibody (IgM); hepatitis C RNA; cytomegalovirus IgM antibody; Epstein-Barr viral capsid antigen IgM antibody (or if unavailable, obtain heterophile antibody or monospot testing); hepatitis E IgM antibody. In those with underlying chronic hepatitis B at study entry (identified by positive hepatitis B surface antigen) quantitative hepatitis B DNA and hepatitis delta antibody. If hepatitis delta antibody assay cannot be performed, it can be replaced with a PCR of hepatitis D RNA virus (where needed) [Le Gal, 2005].

Phase 1-2 Liver chemistry increased monitoring criteria with continued therapy

Liver Chemistry Increased Monitoring Criteria and Actions with Continued Study Intervention Liver Monitoring Event			
Criteria	Actions		
ALT $\geq$ 3 x ULN but $\leq$ 5 x ULN and	• Notify the study PI (cc: MCW Multisite Team email)		
total bilirubin <2 x ULN or INR	within 24 hours (refer to reporting section) of learning		
≤1.5, without symptoms believed	of the abnormality to discuss participant safety.		
to be related to liver injury or	• Participant can continue study treatment.		
hypersensitivity and who can be	Participant must return weekly for repeat liver		
monitored weekly for four weeks.	chemistries (ALT, AST, alkaline phosphatase, bilirubin		
	and INR) until they resolve, stabilize, or return to within		
	baseline.		
	• If at any time participant meets the liver chemistry		
	stopping criteria, proceed as described above.		
	• If, after four weeks of monitoring, ALT <3 x ULN,		
	bilirubin <2 x ULN and INR 1.5, monitor participants		
	twice monthly until liver chemistries normalize or return		
	to within baseline.		

#### **Infusion-Related Reactions Stopping Criteria**

Premedication is not required prior to infusion unless deemed medically appropriate by the investigator following evaluation of infusion-related reactions (IRRs). Premedication should be considered for any participant who experienced an IRR at first or any subsequent infusion with belantamab mafodotin. For infusion reactions of any grade/severity, immediately interrupt the belantamab mafodotin infusion and manage symptoms. Once reaction symptoms resolve, resume the infusion at a reduced rate. Premedication may be required with subsequent infusions.

A participant who experiences a grade 4 IRR associated with belantamab mafodotin should be permanently withdrawn from the study treatment and enter follow-up.

Short Title: MCW EMBRACE TRIAL 50 Version No.: 3
Version Date: 12/29/2022

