of dosing)	Grade 4 (Platelet count less than 25,000/mcL)	
 
Withhold the belantamab mafodotin dose. Consider restarting with one dose-level reduction if recovered to ≤ grade 3, only if there is no active bleeding at time of treatment restart.
 
If thrombocytopenia is considered disease related, is not accompanied by bleeding, and recovers with transfusion to >25 x10^9/L, continuing treatment with dose reduction may be considered after discussion with the sponsor-investigator (cc: MCW Multisite Team email).
 

Febrile neutropenia	Grades 3–4 Defined as: single temperature of 38.3°C, or sustained 38°C for >1 hour AND ANC <1.0×10°/L	
 
Withhold belantamab mafodotin and immediately hospitalize participant with appropriate management, per local institutional guidance.
 
Consider additional supportive treatment per local practice (e.g., growth factors).
 
Upon recovery, consider a 25% dose reduction of belantamab mafodotin, if neutropenia was drug related.
 

Afebrile neutropenia	Grades 3–4 (Defined as ANC <1.0x10  /L)	
 
If noted on day 1 of any cycle, withhold belantamab mafodotin dose.
 
Resume belantamab mafodotin at preheld dose once neutropenia recovers to grade ≤2 (ANC ≥1.0x10^9/L) on day 1 of a subsequent cycle.
 
Prophylactic antibiotics, per physician discretion and local institutional guidance. Consider growth factors.
 
Local guidance must be followed for hematological monitoring if more conservative than the protocol SoA specifications.
 
In cases of frequent recurrent neutropenia (ANC<1.0x109/L), consider dose reduction of belantamab mafodotin.
 

Infusion reaction b	Grade 2	Stop the infusion, provide medical treatment and continue at slower rate after resolution to grade 0–1.

Short Title: MCW EMBRACE TRIAL 41 Version No.: 3
Version Date: 12/29/2022

Toxicity	Grade/description of toxicity	Action	
	Grade 3	Further treatment with belantamab mafodotin needs to be discussed with sponsor-investigator. Continuation only allowed after recovery to ≤grade 1 and with premedication, and extension of infusion time to 2–4 hours. Any future infusion needs to be premedicated.	
	Grade 4	Permanently discontinue.	
	Grade 1	Continue treatment at the full dose when toxicity resolves to grade < 1.	

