#### Table 3b. Dose modifications (other)

\*The following actions should be taken only if toxicity may be possibly attributed to belantamab mafodotin.

	Severity	Management	Follow-up
	Grade 1	
 
Administer symptomatic treatment as appropriate.
 
Continue study drug(s).
 
	Provide close follow-up to evaluate for increased severity, no dose modification necessary
Events Not Otherwise Specified	Grade 2	
 
Administer symptomatic treatment.
 
Investigate etiology.
 
Consider consulting subspecialist, and/or diagnostic procedure.
 
	
 
Symptoms resolved in ≤7 days:
 
Continue after resolution at the current dose
 
Symptoms ongoing >7 days or worsening:
 
Consult study PI (cc: MCW Multisite Team email)
 
Delay study drug, or consider one dose level reduction. If recovery takes >3 weeks, consult with study PI (cc: MCW Multisite Team email)
 
If symptoms continue or worsen to grade 3–4, see below.
 

	Grade 3	
 
Provide appropriate medical treatment.
 
Consider consulting subspecialist.
 
	
 
Consult study PI (cc: MCW Multisite Team email).
 
Delay treatment till recovery to grade ≤ 1.
 
Consider dose reduction.
 
 Exceptions: Participants who develop grade 3

<sup>b If symptoms resolve within one hour of stopping infusion, the infusion may be restarted at 50% of the original infusion rate (e.g., from 100 mL/hr to 50 mL/hr). Otherwise, dosing will be held until symptoms resolve and the participant should be premedicated for the next scheduled dose.

		toxicities which respond to standard treatment and resolve to grade ≤ 1 within 48 hours may continue treatment at scheduled or reduced dose.
Grade 4	
 
Provide appropriate medical treatment.
 
Consider consulting subspecialist.
 
	Interrupt treatment.     Further treatment with belantamab mafodotin only allowed on individual basis if it is agreed between the site investigator and overall study PI (via email, cc: MCW Multisite Team email) that benefits outweigh the risks for a given participant

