### 7.1.6 Handling and Drug Accountability

Belantamab Mafodotin for Injection, 100 mg drug product is supplied as a lyophilized powder for solution for infusion. Detailed instructions for preparation and administration of doses are provided in the site instruction manual. Prepared doses of belantamab mafodotin in the range of 0.2 – 2.0 mg/mL in 0.9% NaCl should be used as soon as possible and no later than 6 hours from the time of dose preparation including administration because the product does not contain an antimicrobial preservative.

The recommended storage condition is 2-8°C, protected from light. The expiry date, where required, is stated on the product label. Before use, remove the drug product vial(s) from the refrigerator and allow to stand for approximately 10 minutes to reach room temperature (68°F to 77°F [20°C to 25°C]).

Each vial of the drug product is reconstituted with 2.0 mL of sterile WFI before use. Once reconstituted, the drug product solution in vial(s) should be used to prepare the dose as soon as possible. If the reconstituted solution is not used immediately, store the vial(s) refrigerated at 36°F to 46°F (2°C to 8°C) or at room temperature (68°F to 77°F [20°C to 25°C]) for up to 4 hours in the original container. Do not freeze. Discard the reconstituted DP vial(s) if not used to prepare diluted dosing solution within 4 hours.

Visually inspect the reconstituted solution for particulate matter and discoloration. The reconstituted drug product solution in vial should be clear to opalescent, colourless to yellow to brown liquid. Discard the reconstituted vial if extraneous particulate matter other than translucent to white proteinaceous particles is observed.

GSK2857916 (belantamab mafodotin) dose rounding instructions:

Participant's weight in kilograms (kg) should be entered to one decimal place and the total dose (mg) will be calculated to two decimal places.

Example:

```
Total Dose (mg) = 97.2 \text{ kg} * 1.9 \text{ mg/kg}
Total Dose (mg) = 184.68 \text{ mg}
```

The quantity of vials dispensed will depend on the participant's weight and dose level.

For dose preparation, withdraw calculated volume of reconstituted DP from the vial(s) for each dose and add to 250 mL IV bag containing 0.9% sodium chloride. The diluted dosing solution is stable at 0.2 mg/mL to 2 mg/mL in 0.9% sodium chloride for injection for a maximum of 6 hours (including infusion time) when stored at room temperature (68°F to 77°F [20°C to 25°C]).

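### Section 5.3's instruction to resume after an infusion reaction omits Table 3a's grade 3 conditions and footnote b's one-hour condition

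*Combined protocol and SAP*

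**What the plan says.** Three places in the protocol tell a site what to do after an infusion reaction.

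**Section 5.3, Infusion-Related Reactions Stopping Criteria.** The instruction opens with "For infusion reactions of any grade/severity, immediately interrupt the belantamab mafodotin infusion and manage symptoms" and continues "Once reaction symptoms resolve, resume the infusion at a reduced rate". On later doses it says "Premedication may be required with subsequent infusions". The next paragraph makes one exception: "A participant who experiences a grade 4 IRR associated with belantamab mafodotin should be permanently withdrawn from the study treatment and enter follow-up".

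**Table 3a, infusion-reaction rows.** These are set out by grade.
- Grade 2: "Stop the infusion, provide medical treatment and continue at slower rate after resolution to grade 0–1".
- Grade 3: "Further treatment with belantamab mafodotin needs to be discussed with sponsor-investigator". The row then permits continuation only once the reaction has fallen to grade 1 or below, with premedication and with the infusion lengthened to 2–4 hours. It makes premedication compulsory for all later infusions.
- Grade 4: permanent discontinuation.

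**Footnote b to Table 3a.** It is keyed to the infusion-reaction entry as a whole, not to one grade: "If symptoms resolve within one hour of stopping infusion, the infusion may be restarted at 50% of the original infusion rate". If symptoms take longer, dosing is held until they resolve, and the participant is to be premedicated at the next scheduled dose.

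**The concern.** Section 5.3 excepts only grade 4, so a grade 3 reaction falls under its general instruction to resume. Table 3a allows a grade 3 participant to continue only when several conditions are met. Staff who look up one place and staff who look up the other would act differently, and both could cite the protocol.

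Infusion-related reactions are on the Section 6.4 list of adverse events of special interest, and the decision is made at the chairside. What is at stake is first participant safety: whether a grade 3 participant is re-exposed with or without Table 3a's conditions. It is secondarily consistency, because in a single-arm trial planned at three sites, the handling of these reactions, and the exposure that follows, could depend on which page a site uses.

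**Working it through.** No arithmetic decides this point. The check is a grade-by-grade comparison of the three texts.

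| Situation | Section 5.3 | Table 3a row | Result |
|---|---|---|---|
| Grade 2 | Interrupt, manage, resume more slowly once symptoms resolve | Stop, treat, continue more slowly at grade 0–1 | Broadly agree |
| Grade 3 | Same general instruction; later premedication is a possibility | Sponsor-investigator discussion, recovery to grade 1 or less, premedication, 2–4 hour infusion; later premedication compulsory | Conflict |
| Grade 4 | Permanent withdrawal from study treatment (next paragraph) | Permanent discontinuation | Same outcome |

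Grade 1 is not counted. In the text available for review, no grade 1 row can be assigned with certainty to infusion reactions, and this may be an effect of how the table was read.

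**Grade 3, element by element.**
1. Discussion with the sponsor-investigator: needed in Table 3a, absent from Section 5.3.
2. Premedication before continuing: a condition in Table 3a. Section 5.3 does not make resuming depend on it.
3. Premedication at later infusions: compulsory in Table 3a, a possibility in Section 5.3.
4. Infusion time: 2–4 hours in Table 3a, an unspecified slower rate in Section 5.3.
5. Recovery threshold: grade 1 or less in Table 3a, resolved symptoms in Section 5.3. These can be read together.

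**Footnote b against Section 5.3.** Section 5.3 makes resumption depend on symptoms resolving and sets no time limit. Footnote b permits the half-rate restart when they resolve within one hour. Its clause for slower resolution holds dosing until symptoms resolve and then mentions the next scheduled dose. It does not say whether the rest of the interrupted dose may be given.

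**Footnote b against the grade 3 row.** Because the footnote names no grade, its scope matters. Halving the rate doubles the infusion time. From the nominal 30 minutes of Section 5.1, a full dose would take 2 × 30 = 60 minutes, which is short of 2–4 hours. Half rate gives a 2–4 hour full infusion only if the starting infusion was set for 1–2 hours. Sending sites to Table 3a would therefore not settle grade 3 unless the footnote's scope is also stated.

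**Precedence.** Section 5.2.2 sends readers to the tables for drug-related events, but the infusion-reaction text in Section 5.3 does not refer to Table 3a, and no passage ranks one over the other. The cross-references on toxicity dose reduction also differ: the Protocol Summary cites Section 5.3, and Section 5.1 cites Section 5.2.

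**The case against.** The best defence is that Section 5.3 is a general statement and Table 3a the specific rule. Much of the two can be read together: a 2–4 hour infusion is a slower one, resolved symptoms are no looser than recovery to grade 1, and a general remark that premedication may be needed leaves room for it to be compulsory at grade 3. Table 3a also allows continuation, so the texts are not opposites. This narrows the conflict, but it does not supply the sponsor-investigator discussion or the premedication condition to a reader of Section 5.3, and no stated rule makes the table prevail.

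Three stronger readings are tempting, and the documents do not support them.

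- *That grade 4 is also contradictory.* The phrase covering all grades is loose, but the next paragraph of Section 5.3 withdraws grade 4 participants from treatment, as Table 3a does.
- *That footnote b postpones any reaction lasting over an hour to the next cycle, nominally 56 days.* The hold is worded to end when symptoms resolve, and the mention of the next dose attaches to premedication. Loss of the interrupted dose is one reading of an unclear clause.
- *That footnote b's example, 100 reduced to 50 mL/hr, is an error.* The preparation instruction is to "add to 250 mL IV bag containing 0.9% sodium chloride", and 250 mL over 0.5 hours is 500 mL/hr. But the figures are offered only to illustrate a 50% cut. Table 3a's 2–4 hours gives 250/4 = 62.5 to 250/2 = 125 mL/hr, a range that includes 100. Even a whole bag at 50 mL/hr takes 250/50 = 5 hours, inside the 6-hour room-temperature limit in Section 7.1.6. No stated limit is breached.

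It is also fair to say that no effect on the primary endpoint has been shown.

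**Conclusion.** The point holds for grade 3 and for the one-hour condition. Section 5.3, as written, directs a restart after a grade 3 reaction without the sponsor-investigator discussion, the compulsory premedication or the 2–4 hour infusion that Table 3a requires. Footnote b adds a time condition that Section 5.3 lacks and leaves the fate of an interrupted dose open. Of the three grades clearly set out in Table 3a, one is in conflict, grade 2 broadly agrees, and grade 4 agrees in outcome.

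The number of participants affected cannot be given, because the documents state no expected frequency of infusion reactions by grade. The case for acting rests on participant safety, not on a demonstrated effect on the trial's estimates. It assumes that a site may act on Section 5.3 without also consulting Table 3a, which the missing cross-reference makes plausible. No view is taken on which clinical rule is right.

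**What to change.** Reconcile Section 5.3, the infusion-reaction rows of Table 3a and footnote b into one grade-specific instruction, and have the other places refer to it. The reconciled text should state:
- what applies at each grade, with the grade 4 exception placed so that the wording on all grades no longer appears to include it;
- to which grades footnote b's one-hour condition and half-rate restart apply;
- what happens to the interrupted dose when symptoms last more than one hour.

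The clinical team decides which rule stands. The cost is a wording amendment, with its review, and a memo to sites. No procedures, visits or participants are added.
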